7.2.3 CLASSIFICATION OF AN ADVERSE EVENT

7.2.3.1 SEVERITY OF EVENT

For adverse events (AEs), the following guidelines will be used to describe severity:

- **Mild** – Events require minimal or no treatment and do not interfere with the subject's daily activities.
- **Moderate** – Events result in a low level of inconvenience or concern with the therapeutic measures. Moderate events may cause some interference with functioning.
- **Severe** – Events interrupt a subject's usual daily activity and may require systemic drug therapy or other treatment. Severe events are usually potentially life-threatening or incapacitating. Of note, the term "severe" does not necessarily equate to "serious."

7.2.3.2 RELATIONSHIP TO STUDY INTERVENTION

All adverse events (AEs) must have their relationship to study intervention assessed by the clinician who examines and evaluates the subject based on temporal relationship and his/her clinical judgment. The degree of certainty about causality will be graded using the categories below. In a clinical trial, the study product must always be suspect.

- **Related** – The AE is known to occur with the study intervention, there is a reasonable possibility that the study intervention caused the AE, or there is a temporal relationship between the study intervention and event. Reasonable possibility means that there is evidence to suggest a causal relationship between the study intervention and the AE.
- **Not Related** – There is not a reasonable possibility that the administration of the study intervention caused the event, there is no temporal relationship between the study intervention and event onset, or an alternate etiology has been established.

7.2.3.3 EXPECTEDNESS

The Principal Investigator will be responsible for determining whether an adverse event (AE) is expected or unexpected. An AE will be considered unexpected if the nature, severity, or frequency of the event is not consistent with the risk information previously described for the study intervention.

7.2.4 TIME PERIOD AND FREQUENCY FOR EVENT ASSESSMENT AND FOLLOW-UP

The occurrence of an adverse event (AE) or serious adverse event (SAE) may come to the attention of study personnel during study visits and interviews of a study subject presenting for medical care, or upon review by a study monitor.

All AEs including local and systemic reactions not meeting the criteria for SAEs will be captured on the appropriate Adverse Event Reporting form. Information to be collected includes event description, time of onset, Principal Investigator's assessment of severity, relationship to study intervention, and time of resolution/stabilization of the event. All AEs occurring while on study must be documented appropriately regardless of relationship. All AEs will be followed to adequate resolution.

Any medical condition that is present at the time that the subject is enrolled will be considered as baseline and not reported as an AE. However, if the study subject's condition deteriorates at any time during the study, it will be recorded as an AE.

Changes in the severity of an AE will be documented to allow an assessment of the duration of the event at each level of severity to be performed. AEs characterized as intermittent require documentation of onset and duration of each episode.

The Study Coordinator will record all reportable events with start dates occurring any time after informed consent is obtained until 7 (for non-serious AEs) or 30 days (for SAEs) after the last day of study participation. At each study time point, the Study Coordinator will inquire about the occurrence of AE/SAEs since the last assessment.

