3 STUDY DESIGN

3.1 OVERALL DESIGN

This is a cluster randomized trial in which home visitors (n=18 anticipated) employed by our partner (First Teach Home Visiting Program) will be randomly assigned to deliver the home visiting standard curriculum with or without HABITS (n=9 home visitors in each arm).

Caregivers with a child 0-5 years of age who are enrolled in the First Teacher Home Visiting program and who have completed their initial 90-day home visiting program benchmark testing will constitute our initial recruitment pool (>50% African American, 40% White, <10% other/multiple race). First Teacher Home Visiting Program enrolls caregivers with young children in their free and voluntary services through community outreach. In order to be eligible for home visiting services, families must have a social risk factor such as poverty, social isolation, lack of material and social support, lack of transportation and limited education and literacy.

Home visitors will approach their families who are potentially eligible to introduce the study, gauge interest, and screen interested families for eligibility. Designated study staff determine of families are eligible based on the completed screening form and inclusion/exclusion criteria. Home visitors are informed of family's eligibility and notify the family. Eligible families are then introduced to a blinded study assessment worker who schedules the enrollment and baseline visit.

Assessment workers (who are distinct from home visitors and masked to group assignment) will be responsible for completing informed consent, enrolling caregiver-child dyads into the study, and completing Visit 1 (baseline), Visit 2 (6-month), and Visit 3 (12-month) assessments.

After completing Visit 1 (baseline) assessment procedures, families will be told by their home visitor which study arm they have been allocated to, for those in the HABITS intervention arm (i.e., home visiting standard curriculum with HABITS) will begin receiving the HABITS intervention at their home visits for 12-months.

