8.3.4 SAFETY ANALYSES

Rates and severity of adverse events will be summarized using descriptive statistics and compared between study arms by Chi-square test of equal proportions.

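### AE severity is compared between arms, but the plan neither masks the role that grades it nor has it graded before the intervention-related judgements

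*Combined protocol and SAP*

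**What the plan says.** **Masking.** Section 3.1 describes one masked group: "Assessment workers (who are distinct from home visitors and masked to group assignment". They obtain consent and carry out the baseline, 6-month and 12-month visits. Sections 4.4 and 7.1 repeat that these staff are blinded. No section states the masking status of the Study Coordinator or the Principal Investigator. Families learn their arm from the home visitor after the baseline visit (Section 3.1).

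**Asking and recording.** Section 7.2.4 gives both tasks to the Study Coordinator: "At each study time point, the Study Coordinator will inquire about the occurrence of AE/SAEs since the last assessment", and "The Study Coordinator will record all reportable events with start dates occurring any time after informed consent is obtained".

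**Severity.** The three grades in Section 7.2.3.1 turn on how far an event interferes with functioning or daily activity. Section 7.2.4 says the AE form holds the Principal Investigator's "assessment of severity, relationship to study intervention, and time of resolution/stabilization of the event".

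**Other judgements.** Section 7.2.3.3 gives expectedness to the Principal Investigator, measured against the known risks of the intervention. Section 7.2.5 requires the Principal Investigator's report of a serious event to include a causality assessment. Section 7.2.3.2, however, says that relationship for all AEs is "assessed by the clinician who examines and evaluates the subject based on temporal relationship and his/her clinical judgment".

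**Use.** Section 8.3.4: "Rates and severity of adverse events will be summarized using descriptive statistics and compared between study arms", by chi-square test.

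**A masked source that is not used.** Section 7.1 has blinded staff give a Medical Changes Survey at Visits 2 and 3. No section links the answers to the AE form.

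**The concern.** A severity grade that depends on judgement is protected from bias when the grader does not know the arm, or at least fixes the grade before turning to questions that bring the intervention to mind. The plan provides for neither. The role that grades severity also decides whether an event was expected under HABITS and whether HABITS may have caused a serious event. Nothing says that severity comes first.

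If the arm is known, a tendency to grade HABITS events down would hide harm, and a tendency to grade them up would create a false signal. Either would enter the chi-square comparison in Section 8.3.4 directly. The trial already runs a masked assessment team, but the AE pathway does not draw on it.

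**Working it through.** The point rests on the text. The plan states no figure to reproduce, so the check sets the roles side by side and then illustrates size under assumptions.

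**Step 1: role against masking statement**

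| Task | Role | Section | Masking stated? |
|---|---|---|---|
| Visits 1 to 3, including weight | Assessment worker | 3.1, 7.1 | Yes, masked |
| Medical Changes Survey, Visits 2 and 3 | Assessment worker | 7.1 | Yes, masked |
| Asking about and recording AEs | Study Coordinator | 7.2.4 | Not stated |
| Severity | Principal Investigator | 7.2.4 | Not stated |
| Expectedness | Principal Investigator | 7.2.3.3 | Not stated |
| Causality of serious events | Principal Investigator | 7.2.5 | Not stated |
| Relationship, all AEs | Examining clinician (7.2.3.2); Principal Investigator on one reading of 7.2.4 | 7.2.3.2, 7.2.4 | Not stated |

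**Step 2: who judges relationship.** The phrase in Section 7.2.4 can be read in two ways. Either the Principal Investigator assesses both severity and relationship, or only the severity item is the Principal Investigator's and the rest are separate fields on the form. The list also contains event timing, which needs no assessor, so the second reading is open. Section 7.2.3.2 names an examining clinician, a role that appears neither in the Schedule of Activities (Section 1.2) nor among the assessments in Section 7.1. The text does not settle the matter.

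**Step 3: illustration by severity grade.** All inputs are assumptions, because the documents give no AE rate, severity mix or misgrading rate.
- True grades in both arms: 60% mild, 30% moderate, 10% severe.
- A fraction s of one arm's moderate events is recorded as mild. Recorded mild = 60% + s × 30%; recorded moderate = 30% × (1 − s). For s = 20%, 30% and 40% the recorded mix is 66/24/10, 69/21/10 and 72/18/10.
- Pearson chi-square with 2 degrees of freedom at the 0.05 level of Section 8.3; 20,000 simulated trials; events treated as independent.

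Share of trials in which the arms are called different, although the true grades are the same:

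| Events per arm | s = 20% | s = 30% | s = 40% |
|---|---|---|---|
| 20 | 6% | 8% | 11% |
| 30 | 7% | 10% | 15% |
| 70 | 10% | 18% | 31% |
| 140 | 16% | 34% | 57% |

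With no shift the rate is about 5% at 70 and 140 events per arm. With s = 10% and 70 events per arm it is 6%. Against the 70 dyads per group in Section 8.2, 70 and 140 events per arm mean one and two events per dyad.

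**Step 4: illustration by dyad.** If the test instead compares the proportion of dyads with some recorded feature (70 per arm, uncorrected chi-square, exact binomial enumeration, no true difference), a shift of 5 percentage points in one arm gives rejection in 14%, 11% and 10% of trials for base proportions of 10%, 20% and 30%. A shift of 10 points gives 38%, 28% and 24%.

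Both illustrations ignore clustering by home visitor, so even the 5% reference is approximate.

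**The case against.** Three stronger readings are tempting, and the documents support none of them.

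- *The Principal Investigator and the Study Coordinator know the arm.* The plan does not say so; it is silent. Nor does judging relationship force the arm to be known. An assessor can ask whether an event could plausibly result from the intervention without knowing who received it, and the reasonable-possibility and alternative-cause criteria in Section 7.2.3.2 allow that.
- *One person judges both severity and relationship for every AE.* This follows only from one reading of Section 7.2.4. Section 7.2.3.2 points elsewhere, and Section 7.2.5 covers serious events only.
- *The grader has a stake in HABITS as its designer.* The documents do not describe the Principal Investigator in that way.

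The size can also be disputed, and rightly. The larger percentages need one or two events per dyad and regrading of 20 to 40% of one arm's moderate events. Section 2.3.1 calls the intervention low-risk, so events may be few, and a small tendency to regrade hardly moves the test.

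Finally, one obvious remedy has a cost. If the masked workers asked open AE questions, families who know their arm could reveal it to the staff who weigh mothers and children, which would put the primary endpoint at risk. Masking the person who asks would also not remove families' own knowledge of arm, or the extra weekly contacts in the HABITS arm (Section 5.1.2).

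What stands after this: a judgement-based grade is compared between arms, no masking is stated for the role that assigns it, and that role makes at least two intervention-dependent judgements with no order set.

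**Conclusion.** The point holds as a gap in protection, not as proof of unmasked grading. The plan should state the masking status of the two roles and separate the severity grade from the judgements about the intervention. The conclusion depends on the silence of the documents about masking, on the subjective wording of the grades, and on the planned between-arm test in Section 8.3.4. It does not depend on the unresolved reading of Section 7.2.4, because expectedness and the causality of serious events already fall to the role that grades severity.

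The likely size is unknown. Under the stated assumptions the false-positive rate ranges from little above 5% when events are few or regrading is slight to 57% in the most extreme case shown. A shift in the other direction could mask a real difference of similar size. For a secondary safety summary in a low-risk behavioural trial, this is a minor-to-moderate point, worth making because the remedy is cheap.

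**What to change.** In Section 7.2.4:

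1. State whether the Principal Investigator and the Study Coordinator are masked to arm.
2. Split the AE form into two parts. The Study Coordinator enters the event description with references to arm, home visitor and HABITS removed. The home visitor must be removed because randomisation is by home visitor (Section 5.2), so that identity reveals the arm. The Principal Investigator grades and locks severity from this description. Relationship and expectedness are assessed only afterwards.
3. Let the Medical Changes Survey answers, already collected by masked staff at Visits 2 and 3, feed the AE form. Do not add new open AE questions for the staff who measure weight.

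Reconcile Sections 7.2.3.2, 7.2.4 and 7.2.5 so that they agree on who judges relationship. This last change is clarification only.

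The cost is protocol wording, a two-part form and a short redaction step per event, using existing staff. Some events, such as an injury during HABITS walking, will still reveal the arm. Reporting by families who know their arm is not changed by any of this.

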2.3 RISK/BENEFIT ASSESSMENT

2.3.1 KNOWN POTENTIAL RISKS

This study involves providing a health behavior intervention to low-income mothers or primary caregivers and children; therefore, the use of children as participants is inherent to the nature of this protocol. If a mother becomes pregnant during the course of the study, we decided not to exclude or discontinue her from the study, as the habit behaviors pose no risk and are likely beneficial to her as well as her unborn child but are also primarily aimed at providing healthy options for the child in the study. The study intervention, which is aimed to improve health behaviors of mothers or primary caregivers and children, is considered low-risk. Additionally, because the study assessments only involve completion of interviews, surveys, vitals, and home food assessments, there is still less than minimal risk to participants. There is a low risk of emotional or psychological discomfort from participants answering personal questions about their eating and activity behaviors. There is also a possible minimal, mild, and temporary risk for physical overexertion due to exercise from increased walking and physical activity. To protect the rights and welfare of these participants, they will be assured that their regular home *visiting* services will in no way be affected by their decision to participate, or not participate, in the study. While we are offering financial incentives to mothers or primary caregivers, these incentives are modest and are only intended to compensate for time completing assessments.

In our preliminary work providing these services, mothers or primary caregivers did not report increased burden from participating in this program. Participants receiving the obesity prevention curriculum were just as likely to meet the benchmark areas defined by Health Resources and Services Administration for evaluating the conventional home visiting program, which suggests that the additional obesity prevention content did not detract from the existing services or over-burden participants receiving the combined program. Also, participants were 27% less likely to discontinue home visiting services when they received the combined home visiting + obesity prevention curriculum as compared to those receiving the conventional program alone in our prior preliminary work.

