7 STUDY ASSESSMENTS AND PROCEDURES

7.1 STUDY ASSESSMENTS

All caregiver-child dyads in the study will complete three (3) assessments: 1) Visit 1 (baseline) at the start of the study, 2) after 6 months (Visit 2), and 3) after 12 months (Visit 3). Blinded assessment staff (assessment workers) will work with families to complete these assessments. Assessments may be done completely in-person at a family's home, a combination of over the phone and in-person, or all remotely with no in-person, physical contact. The visits will include surveys and other measures described below:

- Intake and Demographics Survey (Visit 1 only): Asks questions about age, education, income level, race, medical history.
- The Physical Activity Readiness Questionnaire [PAR-Q] (Visits 1 and 2): Assesses health and ability to do physical activities. If there are any concerns about a caregiver's ability to participate in the walking and movement section of the Habits program, they may be asked to see a doctor about their health before taking part in this section of the program. They will still be able to participate in other parts of the program.⁷⁵
- Behavior Rating Inventory of Executive Function for Adults [BRIEF-A] (All 3 visits): Caregivers will complete this validated questionnaire that asks about attention and how they react to different situations.⁷⁶
- Medical Changes Survey: (Visits 2 and 3): Caregivers will be asked to report any medical or health changes that might have happened since the caregiver and child first started the study.

- Self-Report Behavioural Automaticity Index [SRBAI] (All 3 visits): A four-item automaticity scale that assesses automaticity of HABITS target behaviors for the caregiver and for the caregiver encouraging the child to engage in each target behavior.⁷⁷
- Weight measurements (All 3 visits): Mothers' and child's weight will be measured in duplicate using an electronic scale (Model BWB-800S, Tanita, Portage, MI) according to standard procedures.⁷⁸
- Height measurements (All 3 visits): Caregiver height will be measured in duplicate using a portable stadiometer (Seca 213, Perspective Enterprises) according to standard procedures.⁷⁸ When a height measurement is not possible (due to COVID-19 restrictions), caregivers will be asked to self-report their height.
- Patient Health Questionnaire-8 [PHQ-8] (All 3 visits): Assesses caregiver's thoughts and feelings over the last two weeks.⁷⁹

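### The adverse event comparison in section 8.3.4 is a plain chi-square of proportions that takes no account of repeat events, mother–child pairs, time on study or randomisation by home visitor

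*Combined protocol and SAP*

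**What the plan says.** The between-arm safety analysis is one sentence in section 8.3.4: "Rates and severity of adverse events will be summarized using descriptive statistics and compared between study arms by Chi-square test of equal proportions". It does not say whether the unit is a person, a dyad or an event.

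Section 7.2.4 sets what is collected. "All AEs occurring while on study must be documented appropriately regardless of relationship". For one class of event, "AEs characterized as intermittent require documentation of onset and duration of each episode". Recording runs from "after informed consent is obtained until 7 (for non-serious AEs) or 30 days (for SAEs) after the last day of study participation".

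Caregiver–child dyads are enrolled (section 3.1). The AE text speaks only of the subject, but the Medical Changes Survey in section 7.1 asks about changes "that might have happened since the caregiver and child first started the study", so it is reasonable to read AEs as covering both members of the dyad.

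Home visitors are the randomised unit, 9 per arm (section 5.2). Section 8.3.1 gives the mixed model with a home-visitor random effect to primary and secondary outcomes and does not name safety. Section 8.2 assumes an ICC of 0.01, 15% attrition and 140 dyads.

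**The concern.** A chi-square test of equal proportions needs independent yes/no units that are observed for comparable time. AE data here can fail that in four ways:

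- one person can have more than one event;
- a mother and her child share a household and one reporter;
- time on study can differ between people and between arms;
- families of the same home visitor share the allocation, and may share reporting habits.

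The test accounts for none of these. Because the unit is undefined, two analysts could also follow 8.3.4 and report different p-values from the same data. This is the only planned comparison of harms between arms, and its stated error rate would not be the true one.

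**Working it through.** **The plan's own figure.** No number is given for safety. The only power figure is in section 8.2: 59 dyads per group, 0.53 SD, two-sided 0.05, 80% power. The noncentral t gives 81.5%, so it reproduces closely. The ICC and sample size below come from the same section.

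**1. Unit = person with any AE; home visitor ignored.**
Design effect DE = 1 + (m − 1) × ICC. True type I error of a nominal 5% test = 2 × [1 − Φ(1.96/√DE)].

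| Analysis | m per visitor | DE at ICC 0.01 | Type I error |
|---|---|---|---|
| Caregivers or children alone | 140/18 = 7.78 | 1.068 | 5.8% |
| Both pooled | 280/18 = 15.56 | 1.146 | 6.7% |

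Using the synopsis total of 148 instead of 140 gives 5.8% and 6.8%. The ICC of 0.01 was assumed for weight, not for AE reporting. A simulation with stronger assumed heterogeneity (70 dyads and 9 visitors per arm; gamma variances 0.5 person, 0.3 dyad, 0.05 visitor; 0.2 to 3 events per person) gives 7% to 9% for the pooled any-AE test.

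**2. Unit = event; repeats treated as independent.**
Let μ be the mean events per person and CV the between-person coefficient of variation of the rate. With gamma-Poisson counts, the variance exceeds Poisson by φ = 1 + μ × CV². Type I error of an equal-split test on event totals = 2 × [1 − Φ(1.96/√φ)]. Clustering by visitor is left out here. μ and CV are assumptions.

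| μ | CV 0.5 | CV 0.7 | CV 1.0 |
|---|---|---|---|
| 0.2 | φ 1.05: 5.6% | φ 1.10: 6.1% | φ 1.20: 7.4% |
| 1 | φ 1.25: 8.0% | φ 1.49: 10.8% | φ 2.00: 16.6% |
| 2 | φ 1.50: 11.0% | φ 1.98: 16.4% | φ 3.00: 25.8% |
| 4 | φ 2.00: 16.6% | φ 2.96: 25.5% | φ 5.00: 38.1% |

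Simulation with 70 people per arm agrees: 6% to 8% at μ = 0.2, and 8% to 38% at μ from 1 to 4. If events are truly independent, there is no inflation.

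**3. Time on study.**
Section 2.3.1 reports 27% less discontinuation of home visiting with the combined programme in preliminary work. Suppose, as an illustration, that this ratio applies to study attrition, with 15% overall. Then control attrition = 0.15 × 2/1.73 = 17.3%, and HABITS attrition = 0.73 × 17.3% = 12.7%. If leavers go halfway on average, the person-time ratio is (1 − 0.127/2)/(1 − 0.173/2) = 1.026. If they all go at the start, it is (1 − 0.127)/(1 − 0.173) = 1.056. So HABITS would have roughly 3% to 6% more time in which to record events. This is small, but it always runs in one direction.

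**4. Would a count analysis see more?**
Simulated power at a rate ratio of 1.5, 140 people per arm, with the heterogeneity of step 1, any-AE chi-square v t-test on home-visitor mean counts: 29% v 24% at 0.2 events per person, 43% v 45% at 1, 42% v 51% at 2, 38% v 53% at 3. The chi-square figures are flattered by its inflated type I error; the count test stays at 4.3% to 5.5%. Without clustering, at a ratio of 1.4, 70 per arm and 0.2 events per person, power is 12% to 14% v 13% to 15%.

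**The case against.** The strongest reply is that counting people with at least one AE is conventional. It is also the natural reading of a test of proportions, since events divided by people is not a proportion once people average one event or more. On that reading repeat events do no harm, and the large figures in step 2 do not apply. This stands: the 8% to 38% range holds only if events are the unit and are as frequent as assumed. It does not remove the clustering in step 1. Comparing severity across recorded AEs would also make events the unit.

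A reader might go further and infer three things that the documents do not support.

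- *That people will often have several AEs, logged episode by episode.* No AE frequency is given, section 2.3.1 says the intervention "is considered low-risk", and episode-level detail is required only for intermittent AEs.
- *That the chi-square barely sees a rise in the event rate.* With uncommon AEs it does about as well as a count test, and both have low power. The trial is sized on weight change, and 8.3.4 also promises descriptive summaries.
- *That events will be entered twice,* because the Visit 3 survey looks back to study start while the AE inquiry looks back to the last assessment. Nothing says the survey feeds the AE record, and onset time is collected.

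**Conclusion.** The concern holds as a mismatch between the stated test and the design. The certain part is that 8.3.4 names no unit and ignores the randomised cluster. The size is modest on the plan's own inputs: about 5.8% to 6.7% type I error instead of 5% for people with any AE, if the ICC of 0.01 carries over to AE reporting, and 7% to 9% under the stronger heterogeneity assumed in step 1. It grows to about 6% to 8% at 0.2 events per person, or 8% to 38% at 1 to 4, only if events are counted and the assumed between-person variation (CV 0.5 to 1.0) is right. The effect of unequal follow-up is likely to be a few per cent. The case for change is correct error rates and a reproducible result, not a promised gain in power.

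**What to change.** In section 8.3.4:

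- State that the person is the unit, and analyse caregivers and children separately.
- Report both the number of people with at least one AE and events per person-time, by arm.
- Compare event rates with an overdispersed count model (for example negative binomial) with log follow-up time as offset and a home-visitor effect.
- Compare any AE and each person's worst severity with a method that adjusts for home visitor.
- Count each event once, by onset date.
- State the fallback: if events are too few for the model, use a comparison of home-visitor-level summaries, or description alone.

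The cost is SAP wording and standard SAS procedures, with no new data beyond dates already collected. The drawback is that the model may not be estimable with 18 home visitors and rare events, which is why the fallback should be written in advance. Rewording the Visit 3 Medical Changes Survey to look back only to the last visit is optional.
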